7.2 Analysis Variables

This section describes all variables that are used for analysis as well as their source data variables. The other (raw) data variables will be described in section 10. For each variable it is specified how missing values will be handled, if applicable.

7.2.1 Disposition and Protocol Deviations

Disposition parameters are recorded on the eCRF Page ‘End of Study’.

[figure not shown]
Study discontinuations will be defined only for randomized patients.

A patient discontinued the study prematurely, if the question ‘Did the patient complete the study’ was answered as ‘No’. A patient is considered as study completer, if the question ‘Did the patient complete the study’ was answered as ‘Yes’. Otherwise the patient is considered as ‘Ongoing’.

Primary Reason for Study Discontinuation is documented on the eCRF Page ‘End of Study’ in categories ‘Adverse Event’, ‘Lost to Follow-Up’, ‘Decision unrelated to an Adverse Event’, ‘Non-Compliance’, ‘Study terminated by the sponsor’, ‘Study terminated by the investigator’, ‘Other’.

If the date of study discontinuation/study completion as documented on the eCRF page ‘End of Study’ is less or equal than 63 days after the date of first study drug administration as documented on eCRF Page ‘Study Drug Dosing Dates’, discontinuation will be considered as ‘During Treatment Period’, otherwise it will be considered as ‘During Follow-Up Period’.

A patient is considered as Completer of the Treatment Period, if he has a documented Week 8 Visit and did not discontinue the study during the treatment period.

If the eCRF question ‘Was the emergency envelope opened during the study?’ was answered ‘Yes’, the patient will be considered as unmasked.

Protocol deviations will be collected during the study and reviewed during the BDRM according to a separate BDRM plan. During the BDRM, identification of CSR reportable protocol deviations and further categorization of deviations for TLF output will be performed. For the analysis, the CSR reportable protocol deviations as documented in the BDRM minutes will be presented.

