6.1 Analysis Sets

Evaluability for all patients and visits will be determined during a Blind Data Review Meeting, which will take place before unmasking the study for the main objective analysis (i.e. comprising data up to Week 12 Visit).

The Total Set (TOT) will include all patients that have signed informed consent.

The Intent-to-treat Set (ITT) will include all randomized patients and will be used for all exploratory efficacy analyses. All analyses based on the ITT will be summarized by the treatment randomized.

The Safety Set (SAF) will include all randomized patients who receive at least one dose of study medication. This safety population will be used in the analysis of all safety endpoints.

A subset of all patients in the SAF, who entered the Follow-Up Period (SAF-F), will be used in addition to present event-type analyses of the Follow-Up Period. A patient will therefore be considered as entering the Follow-Up Period, if he/she did not terminated the study at or before the Week 8 visit.

All analyses based on the SAF and SAF-F will be summarized by the treatment received.

For the study, both eyes are under investigation. For each patient, a Primary (Study) Eye and a corresponding Secondary Eye will be defined during a Blind Data Review Meeting (BDRM) to enable a patient based presentation of statistical analyses.

For each patient, an eye will be considered as Primary Eye, if

- the eye was treated and
- the investigator considered this eye as qualifying eye.

If both eyes are considered as qualifying eye, the right eye will be chosen.

The other eye will then be considered as Secondary Eye, if the eye was treated. If the other eye was not treated with study medication, no Secondary Eye will be assigned for this patient.

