7.2.5 Measurements of Exposure and Treatment Compliance

The patients will be dispensed a 4 week supply of study medication (1 kit) on the Day 0 visit and at Weeks 4.

Patients will also be instructed to bring back to the clinic at each study visit all the used and unused vials.

Each 4 week kit will be composed of 1 box containing a total of 90 single-use vials of the randomized / assigned medication for daily treatment during 4 weeks and 1 box containing the same number of adaptors and prefilled 0.3 ml WFI syringe.

[figure not shown]
All patients will be dosed one drop (35 µl) three times a day (TID) in each eye during the 8 weeks treatment period.

Exposure

Information on Exposure will be derived from information on eCRF Pages 'Study Drug Dosing Dates' (Date of First Study Drug Administration, Date of Last Study Drug Administration), 'End of Study' (Date of Study Discontinuation/Completion), 'Study Visits' (Date of Week 8) as well as 'Study Drug Dosing and Accountability' (Date of Vial Dispensed/Returned, Days without Treatment).

Exposure will be presented by displaying Duration of Treatment Period, Duration of Follow-up Period, Extent of Exposure and Days on Study Medication, which will be derived as follows

- Duration of Treatment Period:
Week 8 Visit Date or Date of Study Discontinuation/Completion – Date of First Study Drug Administration + 1, whatever is earlier.
- Duration of Follow-Up Period:
Date of Study Discontinuation/Completion – Date of Week 8, for all patients who have completed the treatment period and terminated the study (regularly or prematurely)
For patients who did not complete the treatment period, Duration of Follow-Up Period is set to 0.
Main Objectives Analysis only: if a patient has not completed the study yet, the last documented visit during Follow-Up Period (including unscheduled visits) will be considered for calculating Duration of Follow-Up Period.
- Extent of Exposure (days) = (Date of Last Study Treatment – Date of First Study Treatment Administration + 1),

If Date of Last Study Treatment is missing (e.g. due to Lost to Follow-Up), Date of Study Discontinuation/Completion or Date of Last Study Drug Return (as documented on the eCRF Page ‘Study Drug Dosing and Accountability’) will be used, whatever is earlier.

- Days on Study Medication = Sum of (Date of Vial Returned – Date of Vial Dispensation – Days without Treatment) +1 for all lines in eCRF Page ‘Study Drug Dosing and Accountability’.

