- An AE leading to study discontinuation is defined as an AE where in the eCRF section 'Action regarding Patient' the box 'Patient Withdrawn' is ticked (this should match with the primary reason for early withdrawal of 'Adverse Event' on the End of Study eCRF page).
- An AE is classified as 'Related' to Study Treatment if the relationship to study medication recorded as 'Possible' or 'Probable' or 'Highly Probable'. An AE will be classified as unrelated to study medication if the relationship to study medication was recorded as 'None' or 'Unlikely'. AEs with missing relationship to study treatment will be counted as 'Related' to Study Treatment.
- A Fatal AE is defined as an AE where the outcome is recorded as 'Fatal'.

These definitions will apply accordingly also for the subsequent sub-classes of AEs.

Non Treatment-emergent adverse events (Non-TEAEs)

A Non-TEAE is defined as any AE, which started before the first administration of study treatment. An AE is considered as Non-TEAE, if the eCRF question 'Did the event occur:' was answered with 'Before Treatment Period'.

Treatment-emergent adverse events (TEAEs)

A treatment-emergent adverse event is defined as an AE that started on or after the date of the First Study Treatment Administration. An AE is considered as TEAE, if the eCRF question 'Did the event occurred:' was answered either with 'During Treatment Period' or 'During Follow-Up Period'.

TEAEs in Treatment Period

This is defined as a TEAE (as defined above) that started on or after the date of the First Study Treatment Administration but on or before the Week 8 Study Visit. A TEAE in

Treatment Period will be identified, if the eCRF question ‘Did the event occurred:’ was answered with ‘During Treatment Period’.

TEAEs in Follow-Up Period

This is defined as an TEAE with a start date after the Week 8 Visit. An TEAE will be considered as TEAE in Follow-Up Period, if eCRF question ‘Did the event occur:’ was answered with ‘During Follow-Up Period’.

For listing purposes, treatment day of onset of AE will be derived according to the definition given in section 7.1.

Missing Codes or Incomplete AE start dates:

In the event that coding information will not be available for a specific AE, the event will be presented as ‘Uncoded Event’. However, for final TLFs it is anticipated that all events are coded.

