If the eCRF question ‘Did the event occur:’ was not answered, AEs will be classified to subclass Non-TEAE, TEAE in Treatment Period or In Follow-Up Period based on the AE onset date utilizing the definitions given above. If this is not possible, the event will be classified as TEAE in Treatment Period.

Missing and/or incomplete AE onset dates will be imputed for calculating relative start and stop days only. Dates will be listed as missing/incomplete [with “-“ replacing missing information] but the onset Day listed between square brackets to denote it was calculated based on missing data (i.e. [1]).

Missing and/or incomplete dates will be imputed in a manner that assumes the worst case scenario:

- For a missing start day (but month and year is available), onset is assumed on the first day of the respective month.
- For a missing start month (but year is available), onset is assumed on 1st January of the respective year.
- For a completely missing start date, no imputation will be performed.

If for Non-TEAEs this procedure results in an onset date before date of informed consent, informed consent date will be used.

If for TEAEs in the Treatment Period this procedure results in an onset date before date of first study treatment, date of first study treatment will be used.

If for TEAEs in the Follow-Up Period this procedure results in an onset date before date of Week 8 visit, date of Week 8 visit will be used.

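### The SAP dates discontinuation by a fixed 63-day limit but follow-up entry by the actual Week 8 visit, so a patient who leaves between the two is in the follow-up set, tabulated as a treatment-period dropout, and given 0 days of follow-up

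*SAP*

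**What the plan says.** **Fixed limit.** SAP 7.2.1 assigns a discontinuation to the treatment period if its date "is less or equal than 63 days after the date of first study drug administration", and otherwise to follow-up. The same section calls a patient a completer of the treatment period "if he has a documented Week 8 Visit and did not discontinue the study during the treatment period", so completer status inherits the 63-day limit.

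**Actual Week 8 visit.** SAP 6.1 treats a patient as having entered follow-up, and so as a member of SAF-F, "if he/she did not terminated the study at or before the Week 8 visit". SAP 7.2.10 defines a treatment-period TEAE as one starting from first dose "but on or before the Week 8 Study Visit". Of a follow-up TEAE it says: "This is defined as an TEAE with a start date after the Week 8 Visit". The supportive variable for USPON during treatment (SAP 7.2.7) and the visual field periods (SAP 7.2.9) are also bounded by the Week 8 visit.

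**Durations (SAP 7.2.5).** Treatment duration is "Week 8 Visit Date or Date of Study Discontinuation/Completion – Date of First Study Drug Administration + 1, whatever is earlier". For follow-up the rule is: "For patients who did not complete the treatment period, Duration of Follow-Up Period is set to 0".

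No section says which boundary prevails when the two disagree.

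**The concern.** The two boundaries coincide only when Week 8 falls on day 63. If Week 8 is earlier, a patient who attends it, stops treatment as planned and then leaves by day 63 is on both sides of the line: in the follow-up denominator, but a treatment-period dropout with no follow-up time. The days between Week 8 and exit are then counted in neither duration.

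The protocol supports the visit as the boundary. Its section 8.2 ends study treatment at Week 8, and section 10.2.4 closes the controlled treatment period after that visit.

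At stake is agreement between descriptive tables in a study whose primary objective is safety and tolerability. SAP 10.1 tabulates reasons for discontinuation by study period, SAP 10.5 summarises follow-up duration by arm, and SAP 5.3 requires tables to be cross-checked against each other.

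**Working it through.** Days are date differences from first dose, as in SAP Table 2.

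**Inputs**
- Disposition limit: 63 days (SAP 7.2.1).
- Week 8 window: 49 to 63, target 56 (SAP Table 2).
- Planned arms: 40 and 20 (protocol synopsis).

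**Origin of the limit.** 8 × 7 + 7 = 63, the top of the Week 8 window. The lower end is 8 × 7 − 7 = 49.

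**Rules.** Let w be the day of the Week 8 visit and d the day of discontinuation, with d ≥ w.
- Disposition: treatment period if d ≤ 63, otherwise follow-up.
- Completer: Week 8 documented and d > 63.
- SAF-F: d > w.
- Treatment duration: w + 1.
- Follow-up duration: d − w for completers, otherwise 0.
- Days on study: d + 1.

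The rules conflict when w < d ≤ 63. Each conflict leaves (d + 1) − (w + 1) − 0 = d − w days in neither duration.

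**Cases**

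| w | d | Disposition | Completer | SAF-F | Treatment days | Follow-up days, SAP | Follow-up days, Week 8 boundary |
|---|---|---|---|---|---|---|---|
| 49 | 60 | Treatment | No | Yes | 50 | 0 | 11 |
| 56 | 62 | Treatment | No | Yes | 57 | 0 | 6 |
| 49 | 63 | Treatment | No | Yes | 50 | 0 | 14 |
| 63 | 64 | Follow-up | Yes | Yes | 64 | 1 | 1 |

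The first three rows conflict and the fourth does not. In the first row, 61 days on study less 50 treatment days leaves 11 days unassigned.

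**Extent.** For a given w there are 63 − w exposed exit days: 14 if w = 49, 7 if w = 56 (days 57 to 63), and 0 if w = 63. Over the whole window that is 14 + 13 + … + 1 = 14 × 15 / 2 = 105 conflicting pairs of dates. With the actual Week 8 visit as the boundary throughout, the count is 0. The 105 is a count of possible date pairs and says nothing about frequency.

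**Weight of one patient.** 1/20 = 5 percentage points on vehicle and 1/40 = 2.5 on rhNGF. The documents give no dropout rate. If 1% to 5% of the 60 patients left in the exposed interval (an assumption), that is 60 × 0.01 = 0.6 to 60 × 0.05 = 3 patients.

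**The case against.** The strongest reply is that the limit is not arbitrary, since it is the top of the Week 8 window, and that it touches very little. An affected patient must leave after Week 8 and by day 63, when the next visit is not due before day 77. Much of this stands, and it sets the bounds of the point. Several stronger readings are tempting, and the documents do not support them.

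- *Follow-up TEAEs will certainly appear for such a patient.* SAP 7.2.10 takes the period of each event first from an eCRF question. Only if that is unanswered is the event placed "based on the AE onset date utilizing the definitions given above". SAF-F membership does not depend on that question, so the conflict remains without it.
- *The tolerability signal is corrupted.* The rule labels study exit only. AE-related withdrawal comes from boxes on the AE form, and extent of exposure comes from dosing dates. The USPON definition and the Week 8 ANCOVAs do not refer to the limit.
- *Zero follow-up time distorts follow-up TEAE rates.* SAP 8.1 reports these as percentages of SAF-F patients. Person-time does not enter.
- *An exit on day 66 with no Week 8 visit is wrongly called follow-up.* This is debatable. Day 66 is ten days past the scheduled end of treatment, and such a patient is not a completer in any case.
- *Every patient without a Week 8 visit should be placed in the treatment period.* The visual field rule does this, but SAF-F does not. Applied to disposition, it would turn a patient who missed Week 8, attended Week 12 and left on day 150 into a treatment-period dropout. The 63-day limit handles that patient correctly.

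None of this reconciles SAP 7.2.1 with SAP 6.1 for a patient whose Week 8 visit is documented.

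**Conclusion.** The point holds in a narrow form. For a patient who attends Week 8 and leaves later but by day 63, SAP 7.2.1 gives a period label that contradicts SAF-F membership, and SAP 7.2.5 turns that label into 0 days of follow-up. No visit deviation is needed: an on-schedule Week 8 leaves 7 exposed exit days. The ceiling is 14 days per patient, reached only with Week 8 on day 49 and exit on day 63.

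The damage is limited to three outputs: the disposition-by-period table, the completer flag and the follow-up-duration summary. All are descriptive. The number of patients is probably small, but it rests on an assumed rate because the documents state none. This is a minor inconsistency, but the rule is wrong as written.

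**What to change.** In SAP 7.2.1, make the boundary depend on whether Week 8 took place:

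- Week 8 visit documented with a date: a discontinuation on or before that date belongs to the treatment period, and a later one to follow-up.
- No Week 8 visit, or no date for it: keep the 63-day limit.

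Derive completer status and follow-up duration from this boundary. The first case in the table above then becomes a follow-up discontinuation in a treatment-period completer, in SAF-F, with 60 − 49 = 11 days of follow-up.

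The cost is one sentence in the SAP and one derived variable. It needs no new data and no change to trial conduct.

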7.2.2 Demographics

Demographic characteristics are recorded on the eCRF page “Demography”.

Gender (Male, Female), Ethnicity (‘Hispanic, Latino, Spanish’, ‘Not Hispanic, Latino, Spanish’), and Race (‘White’, ‘Black or African American’, ‘Asian’, ‘Native Hawaiian or Other Pacific Islander’, ‘American Indian or Alaska Native’, ‘Other’) will be analyzed as recorded on the eCRF.

Age (years) at Screening is calculated as:

- $INT((\text{date of informed consent} - \text{date of birth})/365.25)$.
In case of incomplete dates, missing days will be set to 1st and missing months will be set to July.

7.2.3 Glaucoma History and Other Medical/Surgical History

Details on Glaucoma history are recorded on eCRF Page ‘Glaucoma History’.

Analysis variables for Glaucoma history are:

- Presence of chronic primary open angle glaucoma (Yes/No) as documented on the eCRF Page.
- Symptomatic Eyes (Right Eye only, Left Eye only, Both Eyes) derived from the respective eCRF question
- Primary Eye (Right Eye, Left Eye) as defined in the BDRM minutes.
- Secondary Eye (Right Eye, Left Eye, None) as defined in the BDRM minutes

All other medical history is recorded on the “Medical history” eCRF page, whereas surgical history is recorded on the ‘Surgical History’ eCRF Page. Medical history contains information about conditions that a patient might have suffered prior to Baseline visit, or conditions that are ongoing at the time of the Baseline visit. The medical history terms as well as surgical history terms as specified by the investigator will be coded to a Preferred Term (PT) and a System Organ Class (SOC) using the Medical Dictionary for Regulatory Activities (MedDRA) thesaurus.

[figure not shown]
If no coding information will be available for a specific medical/surgical history record, the record will be presented as ‘Uncoded Record’. However, for final TLFs it is anticipated that all medical/surgical history records are coded.

7.2.4 Concomitant Medication

Prior and Concomitant medication data will be collected throughout the study on the ‘Prior / Concomitant Medications’ CRF page.

All medications will have a calculated start and stop day to enable categorization of the medications as ‘Prior’ or ‘Concomitant’:

- Start Day is defined as:

- Start Date of Medication – Date of First Study Treatment Administration + 1
If the Start Date of the Medication is greater than or equal to the Date of First Study Treatment Administration as provided on eCRF page ‘Study Drug Dosing Dates’
- Start Date of Medication – Date of Study Treatment Administration
If the Start Date of the Medication is less than the Date of Study Treatment Administration as provided on eCRF page ‘Study Drug Dosing Dates’
- Stop Day is defined as:
 - Stop Date of Medication – Date of First Study Treatment Administration + 1
If the Stop Date of the medication is greater than or equal to the Date of First Study Treatment Administration as provided on eCRF page ‘Study Drug Dosing Dates’
 - Stop Date of Medication – Date of Study Treatment Administration
If the Stop Date of the Medication is less than the Date of Study Treatment Administration as provided on eCRF page ‘Study Drug Dosing Dates’

‘Prior medications’ are medications that were started before and stopped before or on the day of First Study Treatment Administration as provided on eCRF page ‘Study Drug Dosing Dates’.

‘Concomitant medications’ include all medications that a patient used during the Treatment or Follow-Up Period of the study.

Any medication started prior to First Study Treatment Administration (as provided on eCRF page “Study Drug Dosing Dates”), which was not discontinued on/before Date of First Study Treatment administration, will be considered as ‘Concomitant’. Moreover, any medication started at any time after the First Study Treatment Administration (as provided on eCRF page ‘Study Drug Dosing Dates’) will be considered ‘Concomitant’.

Medications started and stopped on the day of First Study Treatment Administration (as provided on eCRF page ‘Study Drug Dosing Dates’) will be considered to be ‘Concomitant’.

The Investigator Terms (Medication Name, and Indication) will be coded to a World Health Organization Anatomical Therapeutic Chemical (WHO-ATC) Drug class, a WHO-ATC Drug number and a WHO Drug Name (Preferred Term) using the WHO-DRL Drug Dictionary.

Missing Codes or Medication Dates Imputation:

In the event that coding information will not be available for a specific concomitant medication, the concomitant medications will be presented as ‘Uncoded Medication’. However, for final TLFs it is anticipated that all medication records are coded.

Missing and/or incomplete dates for prior and concomitant medications will be imputed for calculating relative start and stop days only. Dates will be listed as missing/incomplete [with “-” replacing missing information] but the Start/Stop Day listed between square brackets to denote it was calculated based on missing data (i.e. [-28], [1], [Ongoing]).

Missing and/or incomplete dates will be imputed in a manner that assumes the worst case scenario.

Technically, incomplete stop dates will be imputed as follows:

- For a missing day (but month and year is available), it will be assumed that medication have been stopped on the last day of the respective month.

- For a missing month (but year is available), it will be assumed that medication have stopped on 31st December of the respective year.
- For a completely missing stop date, the medication will be assumed to be ongoing.

Similarly, incomplete start dates will be imputed as follows:

- For a missing start day (but month and year is available), onset is assumed on the first day of the respective month.
- For a missing start month (but year is available), onset is assumed on 1st January of the respective year.
- For a completely missing start date, no imputation is performed. However, the medication will be considered as concomitant, unless indicated different by stop date.

7.2.5 Measurements of Exposure and Treatment Compliance

The patients will be dispensed a 4 week supply of study medication (1 kit) on the Day 0 visit and at Weeks 4.

Patients will also be instructed to bring back to the clinic at each study visit all the used and unused vials.

Each 4 week kit will be composed of 1 box containing a total of 90 single-use vials of the randomized / assigned medication for daily treatment during 4 weeks and 1 box containing the same number of adaptors and prefilled 0.3 ml WFI syringe.

[figure not shown]
All patients will be dosed one drop (35 µl) three times a day (TID) in each eye during the 8 weeks treatment period.

Exposure

Information on Exposure will be derived from information on eCRF Pages 'Study Drug Dosing Dates' (Date of First Study Drug Administration, Date of Last Study Drug Administration), 'End of Study' (Date of Study Discontinuation/Completion), 'Study Visits' (Date of Week 8) as well as 'Study Drug Dosing and Accountability' (Date of Vial Dispensed/Returned, Days without Treatment).

Exposure will be presented by displaying Duration of Treatment Period, Duration of Follow-up Period, Extent of Exposure and Days on Study Medication, which will be derived as follows

- Duration of Treatment Period:
Week 8 Visit Date or Date of Study Discontinuation/Completion – Date of First Study Drug Administration + 1, whatever is earlier.
- Duration of Follow-Up Period:
Date of Study Discontinuation/Completion – Date of Week 8, for all patients who have completed the treatment period and terminated the study (regularly or prematurely)
For patients who did not complete the treatment period, Duration of Follow-Up Period is set to 0.
Main Objectives Analysis only: if a patient has not completed the study yet, the last documented visit during Follow-Up Period (including unscheduled visits) will be considered for calculating Duration of Follow-Up Period.
- Extent of Exposure (days) = (Date of Last Study Treatment – Date of First Study Treatment Administration + 1),

If Date of Last Study Treatment is missing (e.g. due to Lost to Follow-Up), Date of Study Discontinuation/Completion or Date of Last Study Drug Return (as documented on the eCRF Page ‘Study Drug Dosing and Accountability’) will be used, whatever is earlier.

- Days on Study Medication = Sum of (Date of Vial Returned – Date of Vial Dispensation – Days without Treatment) +1 for all lines in eCRF Page ‘Study Drug Dosing and Accountability’.
If no Vials are dispensed, Days on Study Medication will be set to 0. In case of incomplete/inconsistent documentation on eCRF, Days on Study Medication will be set to Missing.

Compliance

Patient compliance with the study medication will be assessed at each study visit following the dispensing of the study medication for self-administration. For each kit dispensed, the eCRF page ‘Study Drug Dosing and Accountability’ records per return visit:

- Date dispensed
- Kit number received
- Number of vials dispensed
- Date returned
- Number of vials returned
- Number of vials unused
- Number of days without treatment

Compliance will be evaluated according to the following formula:

$$\text{Compliance (\%)} = 100 * \frac{\text{Number of vials dispensed} - \text{Number of unused vials returned}}{\text{Number of expected days on treatment}}$$

The number of expected days on treatment will be set to 56. For each patient, the number of vials dispensed will be derived as the sum of provided numbers in the column “# Vials Dispensed” on the eCRF Page ‘Study Drug Dosing and Accountability; the number of unused vials returned will be derived as the sum of provided numbers in the column “# Vials Unused” on the eCRF Page ‘Study Drug Dosing and Accountability’.

Compliance will be presented categorical as <80%, ≥80%.

